8.2 Site Monitoring

Site visits will be performed on a regular basis by the Data Coordinating Center, to ensure that all regulatory requirements are being met and to monitor the quality of the data collected. Records of Institutional Review Board approvals and patients' charts will be examined on a spot check basis to evaluate the accuracy of the data entered into the database.

9. Risk and Benefit Assessment

9.1 Risks of Nonionic Contrast Agent

Rare risks of the nonionic contrast agent:

- Itchiness
- Rash
- Mild allergic reaction

Very rare risks of the nonionic contrast agent:

- Kidney disease/Contrast-induced nephropathy
- Death

Regarding the risks of contrast material, the rate of adverse reactions with nonionic contrast reagents is 0.2%.⁵⁰ More than 90% of such adverse reactions are allergic-like, very mild (itching, rash) and can be very effectively treated with available drugs (i.e., antihistaminic). Severe reactions occur in 0.02% and one death occurred in 57,739 injections of nonionic contrast material.⁵⁰

Contrast-induced nephropathy (CIN): CIN is expected to be a very rare event among this patient population because patients with already impaired renal function (the strongest predictor of CIN) will not be enrolled). This assumption is strongly supported by our preliminary experience from ROMICAT I. In this study, none of the participants had such an event (0/368).

The very low risk associated with contrast administration has been documented in large scale trials previously. In a randomized trial in 1,196 participants, the incidence rate of CIN defined as an increase in serum creatinine ≥ 1 mg/dL from baseline within 48 to 72 hours following the injection of contrast material was 0 in 359 participants (0%) who had no renal insufficiency and no diabetes mellitus.⁵¹ The risk was 2 in 315 (0.6%) in participants with no renal insufficiency, but who had diabetes mellitus.⁵¹ In this study, the mean volume of contrast-agent administered

was 140 ± 57 mL, which is much higher than the 80 mL of contrast that is administered for a coronary CTA. The risk of CIN may increase if participants in the cardiac interventional arm will be admitted and subsequently undergo further contrast-related diagnostic testing. However, among 209 participants who had both a pulmonary angiogram and a contrast-enhanced spiral CT in the Prospective Investigation of Pulmonary Embolism Diagnosis II, only one participant with diabetes mellitus had a transient episode of acute renal failure characterized by an increase in the serum creatinine level from 1.3 to 2.9 mg/dL.⁵² In this study, the contrast-enhanced CT and pulmonary angiogram were performed within 22 hours. The elevated creatinine returned to normal after administration of intravenous fluids. Thus, overall we expect that the occurrence of CIN will be a rare event in this study.

9.2 Risks Associated With Radiation

While the radiation dosage for CT scanning varies with the part of the body being scanned, the exposure for this examination is approximately between 7 and 17 mSv. This exposure is comparable or less than stress nuclear myocardial perfusion imaging (14–22 mSv) (personal communication with [name], Chairman of the MGH Radiation Safety Committee). In comparison, the average yearly effective dose of natural background radiation is 2.5 mSv,⁵³ the allowed annual exposure of radiation workers is 50 mSv, the allowed exposure in five years is 100 mSv (Table 3).⁵⁴ Thus, even if an enrolled participant would undergo cardiac CT followed by a conventional stress test and selective coronary angiography, the participant would be well below the allowable annual effective dose for radiation workers. The radiation dose from cardiac CT has not been shown to have any adverse effects.

Radiation Exposure

Cardiac CT scanning results in a measurable radiation exposure.⁵⁵ In order to minimize risk for participants in this study we have implemented the following measures:

- Exclude women <40 years of age
- Exclude pregnant and breast feeding women
- Include only women who have a negative pregnancy test
- Application of cardiac CT protocols with the goal to minimize radiation exposure (i.e. use of tube modulation—decrease of radiation exposure by 30% to 50% and prospective triggering in appropriate conditions)
- Review and approval of these CT protocols by the CVCT Core Lab

General Risk Associated with Radiation Exposure

The risk of inducing a malignancy by exposure to radiation is estimated to be 5 cases of malignancy for each 100 individuals exposed to an effective dose of 1 Sv.⁵⁴ The risk is estimated to be higher in infants and children and lower in the elderly. The data, which these estimates are based on, are weak and apply to relatively high levels of radiation exposure⁵⁶ and it remains unclear whether there is a linear relation in lower levels of radiation. Assuming a linear proportion with a low level of radiation, exposure to 1 mSv would lead to 5 malignancies in 100,000 individuals exposed and a dose of 8 mSv would lead to 40 malignancies in 100,000 individuals.⁵⁶ Small amounts of radiation exposure, less than 100 mSv, have not been clearly

shown to have harmful effects. The amount of radiation to which patients will be exposed in this study is less than the amount that is known to cause a measurable harmful effect. Even so, it is generally assumed that a small amount of radiation will have a small chance of producing a harmful effect. These extrapolated risks of the effects of small amounts of radiation are probably overestimates because the estimates ignore the fact that the body can repair the damage done by radiation if the repair mechanisms are not overwhelmed. Radiation is a well-known teratogenic agent and the developing fetus is much more sensitive to radiation than the mother.

Table 3: Estimated radiation exposure for diagnostic tests, background radiation, and exposure limits.

Examination	Effective Dose (mSv)
Chest PA and lateral	0.07
Myocardial Perfusion Imaging (Rest and Stress)	14–22
Thorax CT for the Exclusion of Pulmonary Embolism	7-12
64-Slice CT coronary angiogram	7–17
2-view mammogram	3.0
Natural yearly background radiation	2.5
Max exposure in radiation workers	50

Lifetime Cancer Risk Attributable to Cardiac CT

The absolute cancer risk has been described recently and recommendations have been made⁵⁷. The life time cancer risk from cardiac CT decreases with age and is higher in women than in men, in particular exposure of younger women should be avoided. In our study these recommendations have been incorporated. In comparison, the absolute cancer risk for women to develop breast cancer is 13% and for men to develop colon cancer is 7%, the risk attributed to a cardiac CT scan is 1:466 vs. 1:715 for a 60 year old women and 1:1241 vs. 1:1911 for 60 year old men (for CT without and with tube modulation (female: 21 and 14 mSv, male 15 and 9 mSv respectively).⁵⁷ Thus, the incremental risk induced by cardiac CT compared to the overall risk of the population to develop cancer seems moderate.

Effect of the Implementation of Cardiac CT in the ED Evaluation of Patients with Acute Chest Pain on a Population Basis

The number of CT scans performed in the US was 62 million in 2006⁵⁸. Imaging of the abdomen (50%) and the head (33%) were major single contributors. Specific concern was given to the rise of pediatric CT imaging (from 6% to now 11%) and screening the adult asymptomatic population (i.e. lung, heart). Implementation of cardiac CT in the ED could lead to a small increase of the number of overall CT procedures. However, the effects of the implementation of cardiac CT in the ED would be minimal if 1) other procedures associated with radiation doses would be saved, 2) repeated testing, currently performed in 25% of patients, would be minimized, and 3) rates of unnecessary purely diagnostic cardiac catheterizations would

decrease. Furthermore, already cardiac CT scanning could be performed using single phase acquisition with prospective triggering which would decrease the dose to <5 mSv. In addition, MD over-read will be performed for internal quality control assessment of findings related to CAD and significant cardiac findings such as pulmonary embolism and aortic dissection, to increase awareness to sites of non-coronary findings.

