4.1 Inclusion Criteria

1. Participant must have at least five minutes of chest pain or equivalent (chest tightness; pain radiating to left, right, or both arms or shoulders, back, neck, epigastrium, jaw/throat; or unexplained shortness of breath, syncope/presyncope, generalized weakness, nausea, or vomiting thought to be of cardiac origin) at rest or during exercise within 24 hours of ED presentation, warranting further risk stratification, as determined by an ED attending.
2. Participant must be able to provide a written informed consent.
3. Participants must be <75 years of age, but ≥ 40 years of age.
4. Participant must be able to hold breath for at least 10 seconds.
5. Participant must be in sinus rhythm.

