4.2 Exclusion Criteria

1. New diagnostic ischemic ECG changes (ST-segment elevation or depression > 1 mm or T-wave inversion > 4 mm) in more than two anatomically adjacent leads or left bundle branch block
2. Documented or self-reported history of CAD (MI, percutaneous coronary interventions [PCIs], coronary artery bypass graft [CABG], known significant coronary stenosis [$>50\%$])
3. Greater than 6 hours since presentation to ED to time of consent.
4. BMI >40 kg/m²
5. Impaired renal function as defined by local standard of care - for example, measured serum creatinine >1.5 mg/dL
6. Markedly elevated troponin as defined by local standard of care
7. Hemodynamically or clinically unstable condition (BP systolic < 80 mm Hg, atrial or ventricular arrhythmias, persistent chest pain despite adequate therapy)
8. Known allergy to iodinated contrast agent
9. Currently symptomatic asthma
10. Documented or self-reported cocaine use within the past 48 hours (acute)
11. On Metformin therapy and unable or unwilling to discontinue for 48 hours after the CT scan

12. Contraindication to beta blockers (taking daily antiasthmatic medication): This exclusion only applies to patients with a heart rate > 65 bpm at sites using a non-dual source CT scanner
13. Participant with no telephone or cell phone numbers (preventing follow-up)
14. Participant with positive pregnancy test. Women of childbearing potential, defined as <2 years of menopause in the absence of hysterectomy or tube ligation, must have a pregnancy test performed within 24 hours before the CT scan.
15. Participant unwilling to provide a written informed consent.

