4.3 Recruitment, Screening, and Consent

The research team at each participating site includes the ED attending physician, CT technologist, and research associate(s). The investigator and the research staff will be responsible for the screening, review of participant medical records and investigator-designated data submission. All clinical sites will perform screening Monday through Friday during daytime hours (9am-5pm). Potential subjects will be identified by research coordinator/study nurse staff shortly after admission to the ED usually after the initial ED evaluation consisting of ECG, physical examination, clinical symptoms and presentation, immediate and past medical history has been concluded and screened for eligibility based on a checklist providing inclusion and exclusion criteria.

Eligible subjects will be approached and, if the subject considers participation, the Clinical Research Coordinator (CRC) will describe the rationale of the study, the study procedures with associated risks and benefits. A study physician/study nurse/CRC will speak directly with an ED physician caring for the patient to obtain an assessment of pretest probability for ACS and will verify that the ED physician feels that further observation or diagnostic testing is warranted in this patient.

If the subject agrees and further testing or observation is planned as SOC, key study personnel, typically a study physician or the attending ED physician, will review the study procedures, as well as all potential risks and discomforts and the opportunity to decline or cease participation in the study at any time, answer any remaining questions, and consent the subject.

Patients can be consented but not randomized before the first troponin test result is available. Patients whose initial troponin level is markedly elevated will not be randomized and will not be included in the intent-to-treat population. Patients whose subsequent troponin testing is markedly elevated will be included in the intent to treat population.

Patients can be consented before a pregnancy test is available. However, patients with a positive pregnancy test will not be randomized.

Patients who are not randomized will not be considered part of the intent to treat population.

Informed Consent:

- A potential subject will then be afforded as much time as clinically feasible to review the consent form and decide upon their participation without adversely effecting their ED care, which is typically 1 hour.

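### Section 9.2 lists the exclusion of breast-feeding women as a measure already in place, but no eligibility criterion or randomization rule in sections 4.1 to 4.3 excludes them

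*Protocol*

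**What the plan says.** Section 9.2 of the protocol introduces its list of radiation safeguards with "In order to minimize risk for participants in this study we have implemented the following measures". Three of the five entries concern who may take part: "Exclude women <40 years of age", "Exclude pregnant and breast feeding women", and an entry limiting women to those with a negative pregnancy test. The other two concern the scan protocols and their review.

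Eligibility itself is set in section 4, whose opening text presents the lists in 4.1 and 4.2 as the detailed criteria. On the matters that 9.2 raises, inclusion criterion 3 reads "Participants must be <75 years of age, but ≥ 40 years of age". Exclusion criterion 14 is "Participant with positive pregnancy test", with the added rule that women of childbearing potential "must have a pregnancy test performed within 24 hours before the CT scan". Section 4.3 repeats the pregnancy bar at the point of allocation: "However, patients with a positive pregnancy test will not be randomized". It also says that potential subjects are "screened for eligibility based on a checklist providing inclusion and exclusion criteria".

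**The concern.** Section 9.2 describes what this study does, not general background. An exclusion can only be put into effect through the eligibility rules or a bar on randomization. If the rule is missing from both, the safeguard exists only in the risk narrative.

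Two things are at stake. The first is participant protection: a woman whom the risk assessment says will be kept out can pass screening. The second is the accuracy of what is submitted to the Institutional Review Board, since section 9 tells it that a protection is in place which the operative rules do not deliver. Two sites could also treat the same patient differently, one working from the criteria and the other from section 9.2.

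**Working it through.** No arithmetic applies, because the protocol attaches no number to this point. The check is to take each participant-level measure in section 9.2 and look for the rule that carries it out.

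| Measure in 9.2 | Inclusion criteria 1–5 (4.1) | Exclusion criteria 1–15 (4.2) | Bars on randomization (4.3) |
|---|---|---|---|
| Women under 40 excluded | Criterion 3 | not needed | not needed |
| Pregnant women excluded | – | Criterion 14 | Positive test bars randomization |
| Breast-feeding women excluded | absent | absent | absent |
| Only women with a negative pregnancy test | – | Criterion 14, for women of childbearing potential | Positive test bars randomization |

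1. The exclusion criteria run from 1 to 15 with no gap and no redaction, so the missing rule has not been lost from the list.
2. Besides pregnancy, section 4.3 bars randomization only for a markedly elevated initial troponin.
3. Breast feeding is mentioned nowhere else in the protocol. The amendment summaries, the opening text of section 4 and the imaging guidelines in Appendix A are all silent. Both conflicting texts are current, so this is not a difference between an amendment log and the present wording.
4. Follow one patient through the rules: a breast-feeding woman aged 40 or over and under 75, with a negative pregnancy test, who meets all other criteria. She passes 4.1, passes 4.2 and is not barred by 4.3. Section 10.1 says sites should try to enter every eligible patient.
5. Once randomized, she receives the protocol CT only if allocated to the intervention arm (section 5.1). The planned split is 500 to 500, so the chance is one in two.
6. On size, the accrual table in section 10.1 projects 450 women among 1,000 participants, with no breakdown by age. The protocol gives no lactation rate, so no count can be derived from it. The lower age limit of 40 suggests few or none.

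**The case against.** The strongest reply is about weight. Section 9.2 is protocol text too, and a careful site would honour it. The screening checklist is not part of the protocol, so whether it omits breast feeding is an inference. The entry is half of one item in a five-item list, and no calculation or conclusion in section 9 depends on it. Few women, if any, would be affected.

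Much of this stands, and it sets the severity. It does not remove the discrepancy. The checklist is described as carrying the inclusion and exclusion criteria, and a rule found in neither list cannot be assumed to be on it.

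A reader might also infer more than the text supports:

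- **That such women would be enrolled and scanned as a matter of course.** They could be enrolled. The protocol CT follows only in the intervention arm.
- **That the contrast agent poses a particular danger here.** The list in 9.2 concerns radiation. Section 9.1, on contrast risk, does not mention lactation, and section 9 quantifies no risk to a breast-feeding woman or her infant.
- **That women found to be breast feeding after randomization would go unscanned, producing a deviation in one arm only.** Nothing in the protocol says that such a discovery cancels the scan.
- **That the pregnancy-test entry in 9.2 is a second contradiction, since criterion 14 requires a test only in women of childbearing potential.** It reads most naturally as shorthand for criterion 14, so this is a matter of wording.

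**Conclusion.** The discrepancy is real but minor. Section 9.2 claims an implemented exclusion that sections 4.1, 4.2 and 4.3 do not contain, while the other participant-level measures in the same list each have a counterpart. A breast-feeding woman who is otherwise eligible could therefore be enrolled and, in the intervention arm, scanned.

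There is no material effect on length of stay or any other endpoint. The conclusion rests on two assumptions: that the checklist follows the criteria as section 4.3 describes, and that lactation is uncommon in women aged 40 or over. The second bears on the size of the problem, not on its existence. The documents do not settle whether breast-feeding women ought to be excluded, and this point takes no position on it.

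**What to change.** Reconcile sections 4.2 and 9.2, in one of two ways:

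- add the exclusion as a numbered criterion in 4.2 and on the screening checklist, to be checked before randomization; or
- remove it from the measures that 9.2 describes as implemented, so that the risk statement matches the rules.

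The choice belongs to the sponsor. In the same edit, and as wording only, make the pregnancy-test entry in 9.2 refer to women of childbearing potential as criterion 14 does.

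The cost is one line in 4.2 and one on the checklist, or one line in 9.2. Neither route changes the sample size or any analysis, and any effect on recruitment should be negligible.

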9.3 Other Risks/ Additional Risks of CT Scans

- Discomfort
- Claustrophobia

Risks of IV Needle Placement

- Hemorrhage (hematoma at the injection site)
- Infection (catheter related infection) at the injection site
- Minor discomfort
- Bleeding
- Infection
- Bruising

9.4 Potential Benefits

- Subjects may benefit from randomization into the interventional arm of trial from detection of pathology that may not have been otherwise detected during SOC (e.g., a non-significant coronary stenosis or non-obstructive coronary artery disease that would likely not have been detected by a stress test).
- Data from prior studies indicate that patients in the interventional arm may be earlier discharged and may not have to spend the night in the hospital, there is also the chance that alternative diagnosis such as pneumonia or Pulmonary embolism may be detected - patients may avoid the dual radiation exposure of a CT protocol solely to evaluate for pulmonary embolus followed by a SPECT myocardial perfusion scan.
- Subjects may also benefit in their assessment for long term prognosis and risk for adverse cardiac events and may receive preventive medication as a result of CT.

10. Ethical Considerations

This study is to be conducted according to US and international standards of Good Clinical Practice (International Conference of Harmonization [ICH] guidelines), applicable government regulations, and NIH research policies and procedures.

This protocol and any amendments will be submitted to a properly constituted independent Institutional Review Board (IRB) for formal approval of the study conduct. The decision of the IRB concerning the conduct of the study will be made in writing to the investigator and a copy of this decision will be provided to the ROMICAT PI before implementation of the study.

All study participants in this study will be given an IRB-approved, site-specific ICF describing the study and providing sufficient information for participants to make informed decisions about their participation in this study. The study participant **MUST** be consented with the EC/IRB-approved ICF before the participant is subjected to any study procedures. The IRB-approved ICF **MUST** be signed and dated by the study participant or legally acceptable representative and the investigator-designated research staff obtaining the consent before the participant is subjected to any study procedures.

10.1 Inclusion of Women and Minorities

The participating institutions will not exclude potential participants from participating in this or any study solely based on ethnic origin or socioeconomic status. Every attempt will be made to enter all eligible participants into this protocol and therefore address the study objectives in a patient population representative of the entire English-speaking population at risk for ACS treated by the institution.

Both men and women and members of all ethnic groups are eligible for this trial. In conformance with the National Institutes of Health (NIH) Revitalization Act of 1993, with regard to inclusion of women and minorities in clinical research, the projected gender and minority accruals are shown below:

Table 1: Gender and Minority Accrual Estimates

Ethnic Category	Sex/Gender		
	Females	Males	Total
Hispanic or Latino	66	79	145
Not Hispanic or Latino	384	471	855
Ethnic Category: Total of all participants	450	550	1,000
Racial Category			
American Indian or Alaskan Native	2	2	4
Asian	35	42	77
Black or African American	125	153	278
Native Hawaiian or other Pacific Islander	2	2	4
White	254	312	566
Other/Unknown	32	39	71
Racial Category: Total of all participants	450	550	1,000

11. Adverse Event Reporting

Mistaken discharges are the primary safety issue in this study. All available data indicate that the absence of any detectable CAD (absence of any plaque and stenosis) has a very high NPV for ACS (100% or close to 100%).⁶² Thus, we anticipate that the occurrence of ACS in participants discharged home directly from the ED in the cardiac interventional arm will be also minimal or even zero and similar to the standard of care. If, as demonstrated in ROMICAT I, none of the participants without CAD will have MACE, defined as ACS within 30 days after direct ED discharge, this observation has 90% power to ensure that the true event rate is less than 1%. These assumptions are supported by the results of the ERASE trial, which reported similar and very minimal event rates in each group (only 2 pts with acute MI were mistakenly discharged, 1 in each randomization group, out of 1200 [event rate: 0.0008%]). In this trial, we would have an 80% chance of detecting at least one occurrence of an inappropriately discharged participant if the true rate were over 1%.

At the time of ED discharge, investigators will determine if any adverse events have occurred. An **Adverse Event (AE)** is any untoward medical occurrence in a study participant that may or may not have a causal relationship with the study intervention. An AE can therefore be any unfavorable and unintended sign (including an abnormal laboratory or physiological finding), symptom, or disease temporally associated with the use of a medical treatment or procedure, regardless of whether it is considered related to the medical treatment or procedure (attribution of unrelated, unlikely, possible, probable, or definite). Abnormal results of diagnostic procedures are considered to be AEs if the abnormality:

- results in study withdrawal
- is associated with a serious adverse event (SAE)
- is associated with clinical signs or symptoms
- leads to additional treatment or to further diagnostic tests
- is considered by the investigator to be of clinical significance

Serious Adverse Event (SAE):

An SAE is defined as any untoward medical occurrence that:

- results in death, or
- is life-threatening (at the time of the event), or
- requires inpatient hospitalization or prolongation of an existing hospitalization, or
- results in persistent or significant disability or incapacity, or
- is a congenital anomaly/birth defect.

Reportable Adverse Events

Any untoward medical occurrence that occurs after randomization and prior to discharge from the ED should be reported to the CCC by completing the electronic adverse event case report form.

Immediately Reportable Adverse Events

Any adverse event that is judged by the investigator to be serious AND unexpected AND related to study procedures should be reported within 24 hours of discovery by phone or email to the Coordinating Center. The local Institutional Review Board must also be notified in a timely manner.

Investigators must also report Unanticipated Problems, regardless of severity, associated with the study procedures within 24 hours. An unanticipated problem is defined as follows:

Unanticipated Problem (UP): any incident, experience, or outcome that meets all of the following criteria:

- Unexpected, in terms of nature, severity, or frequency, given the research procedures that are described in the protocol-related documents, such as the IRB-approved research protocol and informed consent document; and the characteristics of the subject population being studied;
